1.3 Risk/Benefits

Major risks of physical exam indicated cerclage that have been reported in previous studies involving singleton pregnancies and include intraoperative rupture of membranes between 4% and 15%, cervical laceration, bleeding, chorioamnionitis (undiagnosed at the time of cerclage or acquired posteriorly to its placement due to exposed membranes into the vaginal flora), failure to place the cerclage due to advanced cervical dilation and failure of the cerclage on prolonging pregnancy with possible pregnancy loss or delivery at a perivable gestational age around 23-26 weeks of gestation.^{23, 24, 29-32} Other risks of cerclage are those associated with anesthesia during the surgical procedure: hypotension, allergy to medications, post spinal headache. After the cerclage placement other risks maybe present during the following weeks as preterm contractions with the cerclage in place may cause laceration of the cervix and bleeding or preterm premature rupture of membranes in which case the cerclage needs to be removed.

Minor side effects include increased noninfectious vaginal discharge: there is a theoretical disruption the vaginal flora associated with foreign object, and minimal discomfort at the time of cerclage removal.

The potential benefits include prolongation of pregnancy, decreasing very preterm delivery (< 28 weeks), very low birth weight (<1500 grams), low birth weight (<2500 grams) and decreased neonatal morbidity (admission to the intensive care unit, respiratory distress, need of intubation, necrotizing enterocolitis, intraventricular hemorrhage), neonatal mortality and long term disease or disability associated with prematurity. These potential benefits are based on results of previous retrospective cohorts of available research in singletons and case reports in twin pregnancies. These benefits significantly outweigh the risk of having a complication related to cerclage placement.

Measurement to decreased risks associated to the cerclage: All of the investigators have received formal training on physical exam indicated cerclage placement. The training and experience of the investigators will minimize the risks associated with cerclage placement.

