3.3 Secondary Study Endpoints

Secondary effectiveness endpoints:

- Gestational age at delivery
- Interval between diagnosis and delivery
- Birth weight of each neonate
- Spontaneous preterm birth rates at less than 24, 28, 32 and 37 weeks gestation
- Spontaneous rupture of membranes before 34 weeks gestation

Secondary safety endpoints:

- Admission to the NICU and length of stay
- Neonatal death before discharge
- Composite adverse neonatal outcome (includes necrotizing enterocolitis, Intraventricular hemorrhage (grade 2 or higher), respiratory distress syndrome, retinopathy, treatment for sepsis and neonatal death)
- Chorioamnionitis (clinical or histological)
- Significant adverse maternal effects including intraoperative rupture of membranes, bleeding and cervical laceration (tear).

4 Subject Selection and Withdrawal

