5.2.2 Expectant management

For those randomized to expectant management, they will continue routine pregnancy care.

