7.1 Sample Size Determination

Calculation of sample size was based on a reduction in the incidence of spontaneous delivery before 34 weeks from 80% in the expectant management group to 40% in the cerclage group, with a power of 80%. To detect this difference at a significance level of 5%, we will need to enroll a total of 46 subjects with 23 subjects in each arm, plus 10% for loss of follow up. Total 52 subjects with 26 subjects in each arm

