7.2 Statistical Methods

The primary outcome is spontaneous preterm birth before 34 weeks of gestation. Secondary outcomes include gestational age at delivery, interval between diagnosis and delivery, birth weight, spontaneous preterm birth rates at less than 24, 28, 32 and 37 weeks gestation, clinical chorioamnionitis and spontaneous rupture of membranes at less than 34 weeks gestation. Secondary safety outcomes include admission to NICU, neonatal death, length of stay in the NICU until discharge home, composite adverse neonatal outcome that includes necrotizing enterocolitis, intraventricular hemorrhage (grade 2 or higher), respiratory distress syndrome, retinopathy of prematurity and treatment for sepsis), and significant adverse maternal effects will include: intraoperative rupture of membranes, chorioamnionitis, postpartum hemorrhage (estimated blood loss and requirement of blood transfusion, cervical tear and uterine rupture).

Statistical analysis will be based on the intention-to-treat principle.

Comparisons between the two groups will be made with the Mann-Whitney U test. Univariate comparisons of dichotomous data will be performed with Fishers exact test. The p values for all hypotheses will be two sided, and p values of less than 0.05 will be considered to be significant. The risk of spontaneous preterm birth before 34 weeks will be quantified by use of the relative ratio and 95% CI. Multivariate analysis will be performed using logistic regression. The risk of spontaneous preterm birth from randomization until 34 weeks will be assessed with Kaplan-Meier analysis, in which gestational age

is the timescale, spontaneous delivery is the event, and elective deliveries are censored. SPSS software package (version 16.0) will be used for all statistical analyses.

8 Safety and Adverse Events

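### Section 7.2 leaves intraoperative rupture of membranes to a between-arm intention-to-treat Fisher test and never estimates its risk per attempted cerclage (minor, cheap to improve)

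*Combined protocol and SAP*

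**What the plan says.** Section 7.2 names the maternal safety outcomes: "significant adverse maternal effects will include: intraoperative rupture of membranes, chorioamnionitis, postpartum hemorrhage", followed by cervical tear and uterine rupture. Section 3.3 also lists intraoperative rupture of membranes, with bleeding and cervical laceration.

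For analysis, 7.2 sets out one route:

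- Analysis set: "Statistical analysis will be based on the intention-to-treat principle".
- Method for yes/no outcomes: "Univariate comparisons of dichotomous data will be performed with Fishers exact test".
- Decision rule: "The p values for all hypotheses will be two sided, and p values of less than 0.05 will be considered to be significant".

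A 95% CI is planned only for the primary outcome. The documents name no safety or as-treated set, no per-procedure denominator and no separate method for harms.

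Two other places matter. Section 1.3 gives, from earlier singleton studies, "intraoperative rupture of membranes between 4% and 15" per cent. Section 5.2.2 describes the comparator: "For those randomized to expectant management, they will continue routine pregnancy care".

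**The concern.** An intraoperative event needs an operation. The expectant arm has none planned, so its count is zero by construction and a null hypothesis of equal rates carries no information. Surgeons and women being counselled need the risk per attempted cerclage, with its uncertainty. Section 7.2 does not ask for that quantity.

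Two consequences follow if the section is applied literally. First, the planned statistic for this harm is a p value that will usually exceed 0.05 at these arm sizes, even if the true rate is at the top of the range the protocol quotes. Second, the intention-to-treat denominator includes women allocated to cerclage who are never operated on, so the percentage shown would fall below the per-procedure rate. Section 4.3 puts an insurance step between allocation and surgery, and section 5.2 lets women withdraw after randomisation. The documents do not say how many this would be.

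**Working it through.** **Inputs.** Arm sizes come from section 7.1: "we will need to enroll a total of 46 subjects with 23 subjects in each arm", raised to 26 per arm for 10% loss to follow-up. The 15% rate is the upper end of the range in section 1.3. The expectant-arm rate is taken as 0, assuming no crossover. The test and the 0.05 level come from 7.2.

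**The plan's own figure.** For 80% v 40%, two-sided 5%, 80% power, pooled variance and no continuity correction:

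n = [1.960·√(2·0.6·0.4) + 0.842·√(0.8·0.2 + 0.4·0.6)]² / 0.4² = 22.3, so 23 per arm. Then 46/0.9 = 51.1, so 52 in total. Both stated sizes reproduce.

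**Step 1: events needed for p<0.05.** With n per arm and k v 0 events, the two-sided Fisher p is 2·C(n,k)/C(2n,k).

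- 23 per arm, k=4: 2·8,855/163,185 = 0.109. With k=5: 2·33,649/1,370,754 = 0.049. Five events are needed.
- 26 per arm, k=5: 2·65,780/2,598,960 = 0.0506. With k=6: 2·230,230/20,358,520 = 0.023. Six events are needed.

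**Step 2: chance of a non-significant result.** This is the binomial probability of fewer than k events among the n women in the cerclage arm.

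| True rate | 23 per arm, P(X≤4) | 26 per arm, P(X≤5) |
|---|---|---|
| 4% | 99.8% | over 99.9% |
| 10% | 92.7% | 96.0% |
| 15% | 74.4% | 81.5% |

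**Step 3: unequal arms.** With n₁ cerclage and n₂ expectant women, the observed table has probability C(n₁,k)/C(n₁+n₂,k). The opposite extreme is added only if it is no more likely. In the three splits below it is more likely, so it is not added and the threshold drops.

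| Cerclage/expectant | Events needed | p | Non-significant at 15% |
|---|---|---|---|
| 25/27 | 4 | 12,650/270,725 = 0.047 | P(X≤3) = 47.1% |
| 24/28 | 4 | 10,626/270,725 = 0.039 | P(X≤3) = 50.5% |
| 25/26 | 5 | 53,130/2,349,060 = 0.023 | P(X≤4) = 68.2% |
| 26/24 | 6 | 0.023 | P(X≤5) = 81.5% |

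One or two women moved between arms can therefore change the answer a good deal. That is a further reason not to rest a safety statement on this test.

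**Step 4: the alternative summary.** Four ruptures among 26 attempted procedures is 15.4%. The Clopper-Pearson limits are the 2.5% point of Beta(4, 23) and the 97.5% point of Beta(5, 22), which are 4.4% and 34.9%. The planned test on 4/26 v 0/26 returns p = 0.110.

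**Step 5: dilution under intention to treat.** The displayed rate is the share operated on times the per-procedure rate. The share is not in the documents, so a range is assumed. At a true 15%:

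| Share operated on (assumed) | Displayed rate | Non-significant, 23 per arm | Non-significant, 26 per arm |
|---|---|---|---|
| 90% | 13.5% | 80.9% | 87.1% |
| 80% | 12.0% | 86.7% | 91.7% |
| 70% | 10.5% | 91.4% | 95.1% |

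**The case against.** The strongest reply is that 7.2 never says this item will be tested. The Fisher sentence is generic and concerns comparisons, and rupture at operation has no comparator, so plain counts would be compatible with the text. This stands in part: applying the test here is an inference. But the section offers no other route and extends its p<0.05 rule to all hypotheses, so an analyst following it has nothing else to use.

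Several stronger readings are tempting and are not supported:

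- *A non-significant result would be reported as no difference or as safe.* The plan says only what counts as significant. A reader shown 4/26 v 0/26 still sees the 15%.
- *All the operative harms are structural zeros.* Only intraoperative rupture strictly needs an operation. Chorioamnionitis, postpartum hemorrhage, cervical tear and uterine rupture can occur in either arm, and a randomised comparison is right for them.
- *A 15% harm would be missed in at least three trials out of four.* This needs equal or nearly equal arms, and even 24/24 gives 71%. Rupture is known at surgery, so loss to follow-up would hardly remove it, and 26 per arm is the more natural size.
- *Dilution is known to be large.* No share is given, section 4.3 says insurers routinely cover the procedure, and no crossover pathway is described.

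It is also fair to say that these events would not be lost. Section 8.3 requires adverse surgical effects to be recorded, section 8.2 lists cerclage-attributable harms for reporting, and section 8.5.1 provides one independent safety review at about 50% delivered. These cover recording and oversight; they do not set the final analysis.

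**Conclusion.** The point holds as a minor one. For intraoperative rupture of membranes, section 7.2 read literally prescribes a comparison with a structural zero and omits the useful estimate, the risk per attempted cerclage. At the planned equal arms, a true 15% would be non-significant in 74% (23 per arm) or 82% (26 per arm) of trials, and in roughly 47-68% for the splits 25/27, 24/28 and 25/26.

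This rests on four assumptions: the generic Fisher sentence governs this outcome; no expectant-arm woman is operated on; all cerclage-arm women are operated on in the headline figures; and the singleton range in section 1.3 is a usable guide for twins. The direction of the dilution is certain if any allocated woman is not operated on and the other arm is unaffected, but its size is unknown. Nothing here touches the primary analysis.

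**What to change.** Add to section 7.2:

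> Intraoperative rupture of membranes, and any listed bleeding or cervical laceration recorded as occurring during the procedure, will be summarised among all women in whom cerclage was attempted, whatever the allocated arm, as a proportion with exact (Clopper-Pearson) 95% CI and no between-arm p value. Maternal outcomes that can occur in both arms (chorioamnionitis, postpartum hemorrhage, cervical tear, uterine rupture) stay in the intention-to-treat comparison.

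A laceration at the procedure would then appear in the per-procedure table and also count as a cervical tear in the randomised comparison; a table footnote should say so. Attempts that end without a suture in place belong in the denominator.

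The cost is two sentences and one table. The denominator is not a randomised one, and the interval will be wide: 0 events in 26 still leaves an upper limit of 13%. Sections 3.3 and 7.2 do not separate bleeding or tears at the procedure from those at delivery, so the team should confirm that the case report form captures timing and whether cerclage was attempted. If it does not, a field for each is needed.

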5.2 Treatment Regimens

Subjects will be randomized in a 1:1 fashion to either receive the physical exam indicated cerclage, or expectant management. Women will still be able to withdrawal from the study after randomization if they feel that either expectant management or cerclage have an unacceptable risk of extreme premature delivery with increased risk of severely handicap children.

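### The adjusted logistic regression has no limit on covariates, with only about 18 to 21 women expected without the event; if cerclage works about as planned, its odds ratio tends to come out too far from 1

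*Combined protocol and SAP*

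**What the plan says.** Section 7.2 takes spontaneous birth before 34 weeks as the primary outcome, compares dichotomous data with Fisher's exact test, and reports the primary effect as a relative ratio with a 95% CI. It then adds: "Multivariate analysis will be performed using logistic regression". The Study Summary has the same sentence, there directly after an odds ratio for the primary outcome. Neither place names the outcome of the model. Because the sentence follows the primary outcome both times, I read it as a model for that outcome.

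The documents give no covariate list, no maximum number of terms, no selection rule, and no penalised or exact method. Section 7.2 names SPSS 16.0 for all analyses.

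Section 7.1 plans a fall "from 80% in the expectant management group to 40% in the cerclage group", "with a power of 80" per cent and "at a significance level of 5" per cent. Section 7.2 adds "The p values for all hypotheses will be two sided", and Section 5.2 has "Subjects will be randomized in a 1:1 fashion". The resulting size is "a total of 46 subjects with 23 subjects in each arm", "plus 10% for loss of follow up", which brings it to 52.

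**The concern.** Maximum-likelihood logistic regression is a large-sample method. When the rarer outcome is scarce and a real effect exists, its coefficients are on average too large in absolute value, and the excess grows with each added term. Here the rarer outcome is *not* delivering spontaneously before 34 weeks. An open-ended model can therefore converge, look ordinary, and still report an inflated treatment odds ratio.

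What is at stake is the size of the adjusted effect. The Study Summary already names the odds ratio as the effect measure, so an adjusted odds ratio could become a quoted result. The trial is also open label, so a covariate list left open until outcomes are known could be shaped by them.

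**Working it through.** **1. The plan's own figure.** Inputs from Sections 7.1, 7.2 and 5.2: 80% against 40%, two-sided 5%, power 80%, 1:1. Pooled normal approximation, mean rate 0.60:

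n per arm = [1.96 × √(2 × 0.6 × 0.4) + 0.842 × √(0.8 × 0.2 + 0.4 × 0.6)]² / 0.4² = (1.358 + 0.532)² / 0.16 = 22.3, so 23 per arm and 46 in all. For loss, 46 / 0.9 = 51.1, so 52 (26 per arm). The plan's numbers reproduce.

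**2. The limiting count.** Expected women without the event:
- 23 per arm: 23 × 0.20 + 23 × 0.60 = 18.4
- 26 per arm: 26 × 0.20 + 26 × 0.60 = 20.8

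Expected events are 27.6 and 31.2, so non-events are the limit. At 10 non-events per parameter the model carries about 2 terms, treatment included (18.4 / 10 = 1.84; 20.8 / 10 = 2.08). At 5 per parameter it carries about 4 (3.68; 4.16).

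**3. The true odds ratio.** Expectant against cerclage: (0.8 / 0.2) / (0.4 / 0.6) = 6.0.

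**4. Simulation with covariates unrelated to outcome** (assumption; 4,000 trials per setting, failed or separated fits excluded). The true odds ratio stays 6.0. Geometric-mean maximum-likelihood estimates:

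| Covariates | 23 per arm | 26 per arm |
|---|---|---|
| 0 | 6.7 | 6.7 |
| 1 | 7.0 | 7.1 |
| 2 | 7.6 | 7.2 |
| 3 | 8.0 | 7.6 |
| 5 | 9.7 | 9.1 |
| 8 | 13.2 | 11.5 |
| 10 | 18.2 | 14.3 |

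Firth-penalised estimates stay between 6.0 and 6.75 throughout. Failed or separated fits were 0.4% to 3.5%.

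**5. Simulation with two prognostic covariates** (assumed odds ratios 2 and 1.3 per SD, any others noise; marginal rates kept at 80% and 40%). The true adjusted odds ratio is then 7.3. It exceeds 6.0 because odds ratios are not collapsible, so 7.3 is the right benchmark. Median maximum-likelihood estimates at 23 per arm, from three runs of 2,500 to 4,000 trials per setting:

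| Covariates | Median odds ratio |
|---|---|
| 1 (one run) | 8.0 |
| 2 | 8.8 to 9.0 |
| 4 | 9.8 to 10.3 |
| 6 | 11.5 to 12.7 |
| 8 | 14.5 to 15.3 |

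At 26 per arm one run gave 8.5, 10.0, 11.1 and 13.5 with 2, 4, 6 and 8 covariates. Firth medians were 6.7 to 7.2, slightly below the truth.

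**6. Accuracy in a single trial** (23 per arm). The root-mean-square error of the log odds ratio with two covariates is 0.96 to 1.04 under maximum likelihood and 0.78 to 0.82 under Firth. With eight covariates it is 2.03 against 1.01. The chance of an estimate more than double the truth is 30% (two covariates) and 50% (eight) under maximum likelihood, against 18% and 21% under Firth.

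**7. No treatment effect.** With a common event rate of 60% or 80% and up to eight covariates, the mean log odds ratio stayed within about 0.03 of zero, and rejection rates were 2.5% to 6.8%.

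**The case against.** The model is one supplementary sentence. The dichotomous comparison is Fisher's exact test and Section 7.2 reports a relative ratio; neither is affected. With two covariates the bias is about 0.18 on the log scale (ln 8.75 − ln 7.33), small beside a standard deviation of about 0.97. The large figures need six to eight covariates, which nothing in the documents proposes. Wald 95% intervals still cover the truth about 93% to 97% of the time. A short fixed list would remove most of the excess, and exact logistic regression or dropping the model would also serve.

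Most of this stands. It limits the point to the adjusted estimate and makes its size conditional on a choice that the plan leaves open. It does not remove the point, because that openness is what permits five or more covariates. Firth estimation also has the smaller error with only two, so penalising does not trade accuracy for less bias.

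A reader might go further and infer that the adjusted odds ratio *will* overstate the benefit of cerclage, or that the model could manufacture one. The documents and the calculations do not support that. The bias is an average tendency: with two covariates the maximum-likelihood estimate fell below the true value in about 41% to 42% of trials. It also needs a real effect; step 7 shows none of note without one.

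**Conclusion.** The point holds in a conditional form. If the effect is near the planned one, ordinary maximum likelihood tends to put the adjusted odds ratio too far from 1. The excess in the median is modest with one or two covariates (about 8 to 9 against 7.3, roughly 10% to 20%) and serious from about five upwards, reaching about twice the true value with eight.

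This assumes that the model is for the primary outcome and that the 80% and 40% rates hold. The number and strength of the covariates are also assumed, because the documents give none; two different covariate assumptions gave the same pattern. The plan should be corrected before outcomes are seen, but the primary test does not depend on it.

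**What to change.** In Section 7.2 and the Study Summary, replace the sentence with wording to this effect: *The supplementary adjusted analysis of spontaneous birth before 34 weeks is a Firth-penalised logistic regression with treatment and at most two baseline covariates, fixed before any outcome is seen, with a profile penalised-likelihood 95% CI. Covariates are not chosen by stepwise or univariate screening.*

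Gestational age at randomisation and cervical dilation are possible covariates. If dilation is used, state its coding for women enrolled on visible membranes alone, since Section 4.1 admits them. If SPSS 16.0 cannot fit the model, name a second package.

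The cost is analysis wording, fewer covariates than an open-ended model, a somewhat less favourable adjusted odds ratio, and possibly a second package. Treatment, visits and sample size do not change.

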3.2 Primary Study Endpoints

Spontaneous preterm delivery at less than 34 weeks gestation

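### Section 7.2 censors elective deliveries in a Kaplan-Meier analysis of a risk, which can overstate spontaneous birth before 34 weeks; no all-cause rate before 34 weeks is planned

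*Combined protocol and SAP*

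**What the plan says.** Section 3.2 gives the primary endpoint as "Spontaneous preterm delivery at less than 34 weeks gestation". Section 7.2 analyses dichotomous outcomes with Fisher's exact test, and the primary risk is to be "quantified by use of the relative ratio and 95% CI".

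Section 7.2 then adds a time-to-event analysis: "The risk of spontaneous preterm birth from randomization until 34 weeks will be assessed with Kaplan-Meier analysis". Gestational age is the timescale, and "spontaneous delivery is the event, and elective deliveries are censored". No competing-risks method, log-rank test or hazard model is named, and the section does not rank this analysis against the others.

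The other preterm-birth rates carry the same restriction to spontaneous birth (section 3.3): "Spontaneous preterm birth rates at less than 24, 28, 32 and 37 weeks gestation". Two timing outcomes in section 7.2 are not restricted by cause: "Secondary outcomes include gestational age at delivery, interval between diagnosis and delivery". The hypothesis at the end of section 1.1 refers to preterm birth before 34 weeks without the word spontaneous, and the Definitions section defines preterm birth by gestational age alone. Neither spontaneous nor elective is defined. The trial is open-label (sections 3.1 and 7).

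**The concern.** Censoring assumes that the woman stays at risk of the event after observation stops. After an elective delivery she does not. The Kaplan-Meier estimate in effect gives her the later experience of women still pregnant, so its complement answers what would happen if elective delivery did not exist. Section 7.2 describes its target as a risk, which is the share of randomized women who deliver spontaneously before 34 weeks. The two differ once an elective birth precedes a spontaneous one. The report could then show two different 34-week risks for the same women, with the larger excess in the arm with more spontaneous births if elective rates are similar.

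The second gap is separate. Staff who know the arm will record whether a birth was spontaneous, and no rule for this is written. Without an all-cause result at 34 weeks, a reader cannot see whether the primary result depends on that classification, or whether the hypothesis as worded in section 1.1 is supported.

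**Working it through.** **Inputs.** Section 7.1 assumes a fall "from 80% in the expectant management group to 40% in the cerclage group", with 80% power, 5% significance, 23 women per arm and 26 after 10% loss. Section 4.1 sets entry between 16 and 23 6/7 weeks. The elective rate is not in the documents and is assumed.

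**The plan's own figure.** With the pooled normal approximation, n = [1.96·√(2·0.6·0.4) + 0.842·√(0.8·0.2 + 0.4·0.6)]² / 0.4² = 22.3, so 23 per arm. Then 46/0.90 = 51.1, or 52 with equal arms. The stated size reproduces and does not depend on the censoring rule.

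**Size of the excess, smooth case.** Let s be the true risk of spontaneous birth before 34 weeks and i the risk of elective birth before 34 weeks. With proportional cause-specific hazards, complete follow-up and all women at risk from the start:

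1 − KM = 1 − (1 − s − i)^(s/(s+i))

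| i, each arm | true 80% reads | true 40% reads | true 40-point difference reads |
|---|---|---|---|
| 0 | 80.0% | 40.0% | 40.0 |
| 5% | 1 − 0.15^(0.80/0.85) = 83.2% | 1 − 0.55^(0.40/0.45) = 41.2% | 42.0 |
| 10% | 1 − 0.10^(0.80/0.90) = 87.1% | 1 − 0.50^(0.40/0.50) = 42.6% | 44.5 |

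**Size at 26 women per arm, two elective births.** Timing decides the result.

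- 21 spontaneous births, crude 21/26 = 80.8%. Both elective births last: 80.8%. Both first: 21/24 = 87.5%. Both after the 19th spontaneous birth: 1 − (7/26)(3/5) = 83.8%.
- 10 spontaneous births, crude 10/26 = 38.5%. Both last: 38.5%. Both first: 10/24 = 41.7%. Both after the 8th: 1 − (18/26)(14/16) = 39.4%.

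**Delayed entry.** On the gestational-age scale, a woman randomized at 23 weeks was not under observation at 17 weeks. If risk sets respect this, the curve estimates the risk for a woman undelivered at the start of the scale, which is not the crude proportion among randomized women. A simulation of 26 women with uniform entry at 16 to 24 weeks, exponential time to delivery, 80% delivered by 34 weeks and no elective births (all assumptions) gave a median excess over the crude proportion of about 6 points. If all women are instead counted at risk from the start, the two agree at 34 weeks, but the early part of the curve counts women who had not yet been randomized.

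**All-cause gap.** Sections 3.2, 3.3 and 7.2 list rates at 24, 28, 32, 34 and 37 weeks, all for spontaneous birth. None lists birth before 34 weeks for any reason.

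**The case against.** Four points on the other side have force.

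First, a reader might infer that the censoring rule biases the primary result. It does not: Fisher's test and the relative ratio use crude proportions.

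Second, a reader might infer that the curve must disagree with the crude proportion once any elective birth occurs, or that the distortion will be large. Neither follows. The excess is zero when elective births come after the last spontaneous birth before 34 weeks. At an assumed 15%, a true 80% reads 92%, but that means 15 of the remaining 20 points, three-quarters of women who escape spontaneous birth, are delivered electively before 34 weeks. The only expectant-management data in section 1.2, seven women, show half delivered before 24 weeks and 85.7% with spontaneous birth by 28 weeks. If spontaneous births come that early, elective births would tend to follow them, and the excess with two elective births is then nearer 0 to 3 points.

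Third, censoring competing events is valid for comparing cause-specific hazards. That stands, but section 7.2 names no such comparison and states a risk as its target.

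Fourth, the all-cause effect is partly visible through "Interval between diagnosis and delivery", gestational age at delivery, birth weight and neonatal outcomes. That also stands, although none gives a risk at 34 weeks. A reader might further infer that reclassifying a few births would overturn the trial. That concerns classification, not censoring, and depends on the chosen split. Near the design rates, 21/26 against 10/26 gives p = 0.004, and two expectant-management births recoded still give 0.025. A borderline 21/26 against 16/26 (p = 0.22) falls below 0.05 only when three cerclage births are recoded (0.040; two give 0.075).

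**Conclusion.** The concern holds in a limited form. For the target that section 7.2 states, censoring elective deliveries is the wrong estimator and can overstate the absolute risk. Under the assumptions above, the excess is about 3 points on 80% and 1 point on 40% at 5% elective births, and about 7 and 3 points at 10%. It is zero with no elective birth before the last spontaneous one. The elective rate and timing are unknown, so the documents do not support a firm figure or a claim that the curve will mislead. Delayed entry is a further source of disagreement that a competing-risks method alone does not remove.

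The absence of an all-cause rate before 34 weeks is a separate and at least equally important gap, because the trial is open-label and the classification is undefined. Its direction is unknown, since births in either arm can be classed as non-spontaneous. The change should be made before analysis; it does not call the primary test or the sample size into question.

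**What to change.** In section 7.2:

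1. Report the absolute risk of spontaneous delivery by 34 weeks as a cumulative incidence (Aalen-Johansen), with non-spontaneous delivery as a competing event. Kaplan-Meier with censoring may stay only for a cause-specific hazard comparison, labelled as such.
2. State how entry is handled: either time from randomization, or gestational age with risk sets that start at randomization. With time from randomization, women reach 34 weeks after about 10 to 18 weeks (34 − 23 6/7 to 34 − 16), so a woman who reaches 34 weeks undelivered should be kept as event-free and not censored on that date. With gestational age, say that the estimate need not equal the crude proportion.
3. Keep the primary endpoint. Pre-specify delivery before 34 weeks for any reason as a sensitivity analysis reported beside it.
4. Write one rule for spontaneous versus non-spontaneous delivery, including where medically indicated births fall, and fix it before analysis. Apply it without knowledge of the arm where existing staff allow.

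The cost is some wording, slightly more analysis and possibly software beyond SPSS 16.0. Labour and delivery data are already to be abstracted (sections 4.3 and 6.5), so the main addition is to make sure the reason for delivery is captured. The all-cause result may be less favourable to cerclage. If the written rule differs from the one behind the 80% and 40% in section 7.1, those rates need re-checking.
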